| Study design: | This is a non-interventional study using existing data including medical chart review. | | |
| Population: | Adult patients (18 years of age or older) with T2D diagnosis, naïve to treatment with empagliflozin or other SGLT2i, DPP4i or GLP1a at index date 1 | | |

| | | | |
|---|---|---|--|
| Name of company: Boehringer Ingelheim | | | |
| Name of finished medicinal product: Jardiance® Synjardy® Trajenta® Jentadueto® | | | |
| Name of active ingredient: empagliflozin linagliptin | | | |
| Protocol date: 12 Dec 2018 | Study number: 1245.187 | Version/Revision: Version 2.0/ Revision 1.0 | Version/Revision date: 11 May 2020 |
| Variables: | 
1. Patient demographics (age, gender, height, weight, BMI, ethnicity)2. Time since diagnosis of Type 2 Diabetes3. Clinical parameters relevant for T2D, CVD, CKD assessment such as HbA1c, blood pressure as valid on index date 14. Comorbidities like cardiovascular diseases and related risk factors such as smoking, overweight and Comorbidities like chronic kidney disease and related risk factors such as smoking, overweight at index date 15. T2D medication the treating HCP newly prescribes at study index date 16. Concomitant T2D medications at index date 17. Concomitant CVD and CKD medications at index date 18. Involvement of other HCPs in treatment decisions at study index date 1 and study index date 29. Relevant socioeconomic parameters such as employment status, family status, type of health insurance at index date 110. Stop date and reason of therapy discontinuation at index date 2 (approximately one year after index date 1) | | |
| Data sources: | Existing patient data (Medical chart review) previously collected by Health care professionals during routine documentation in patients treated for T2D in an endocrinologist, diabetologist or cardiologist office-based setting (nonhospital). | | |
| Study size: | Approximately 4000 patients from 7 countries (Bulgaria, Czech Republic, Hungary, Poland, Serbia, Slovenia, Russia) | | |

| | | | |
|---|---|---|--|
| Name of company: Boehringer Ingelheim | | | |
| Name of finished medicinal product: Jardiance® Synjardy® Trajenta® Jentadueto® | | | |
| Name of active ingredient: empagliflozin linagliptin | | | |
| Protocol date: 12 Dec 2018 | Study number: 1245.187 | Version/Revision: Version 2.0/ Revision 1.0 | Version/Revision date: 11 May 2020 |

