 - sitagliptin
 - saxagliptin
 - vildagliptin
- GLP1a
 - dulaglutide
 - exenatide
 - liraglutide
 - semaglutide
 - lixisenatide
- Reasons for choosing the treatment rated as not relevant at all/ moderately relevant/ highly relevant
 - HbA1c lowering
 - Weight loss

- Cardiovascular risk reduction
- Favorable side effect profile
- Simple dosing / administration
- Guideline recommendation

[figure not shown]
6. Concomitant T2D medications (given as monotherapy or as fix combination with main T2D medication) at study index date 1
 - Metformin
 - Sulfonylurea
 - Acarbose
 - Pioglitazone
 - Insulin
 - others
7. Concomitant CVD and CKD medications at index date 1 (on class level only)
 - Antihypertensives ACEi or ARBs
 - Statins
 - Low dose aspirin
 - Beta blockers
 - Diuretics
8. Involvement of other HCPs in treatment decisions with regard to SGLT2i, DPP4i or GLP1a prescription at study index date 1 and with regard to discontinuation at index date 2 (yes/no; if yes, the medical specialty of the involved physician(s) should be specified)
9. Association of socioeconomic parameters with treatment decisions (such as employment status, family status, type of health insurance) at study index date 1
10. Status of T2D therapy approximately one year (\pm 2 months) after start
 - Stop date, if available
 - Reasons for discontinuation
 - Investigator's decision
 - Patient's request (difficulties in medication handling)
 - Patient's request (financial burden regarding co-payment)
 - Patient's request (other)
 - Lost to follow-up
 - Adverse event (in case of adverse reaction to empagliflozin or linagliptin or fatal adverse event, see [Section 11](#))
 - Death
 - Unknown
 - Other

Primary outcomes

- T2D patients' baseline characteristics when initiating either empagliflozin - or other SGLT2i, DPP4i or GLP1a on top of current antidiabetic treatment by different HCP specialties in CEE countries.

Secondary outcomes

- Burden of comorbidities (prevalence of CVD, CKD and CVD/CKD risk factors) in this T2D patient population at study index date 1
- Actual treatment use at study index date 1 in patients with and without established CVD (Established CV disease defined as acute myocardial infarction (AMI), cardiology intervention, ischemic heart disease (IHD), congestive heart failure (CHF), peripheral arterial disease (PAD), or stroke)
- To describe the association of socioeconomic parameters with treatment decisions at study index date 1

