9.5 STUDY SIZE

No formal sample size calculation is provided for this study. This NIS has been designed to describe, in a real-world setting, usage patterns and outcomes associated with empagliflozin or other SGLT2i or DPP4i or GLP1a in the clinical routine practice. The sample size of approximately 4000 patients is driven by the need to enroll an adequate number of patients to address the mentioned objectives, also across various subgroups, such as physician or country specific analyses. It is aspired to document at least 500 patients in the GLP1a and at least 1000 patients each in the SGLT2i and DPP4i subgroups. However, no formal limitations will be applied for recruitment of patients to subgroups with regard to medication of interest.

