9.9 LIMITATIONS OF THE RESEARCH METHODS

The intention of this NIS is to analyze existing data of T2D patients when initiating on different types of T2D drugs, their comorbidities, their co-medications and socioeconomic factors with possible influence on treatment decisions and treatment duration.

A NIS is the most suitable instrument for obtaining information about the use of medicines in everyday clinical practice.

A possible limitation of the retrospective study design of this NIS is that the time windows of 4 months (index date 1) and of 12 (\pm 2) months (index date 2) will give limited information in the population at a specific point in time. Medication availability might differ between countries due to different reasons (commercial availability, reimbursement status) which will be collected in research question 4 for further data interpretation.

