7. PLANNED ANALYSES

All patients who have received a first prescription of respective study medication will be included in the analysis; this is the prescribed patient set. All analyses at index date 1 will be performed on the prescribed patient set and analyses at index date 2 will be performed on the full analysis set. If patients have missing values for an outcome, those patients will be excluded for that outcome's analysis.

The assessment will be carried out using SAS® software. The statistical characteristics presented in the end-of-text tables will be N / mean / SD / min / median / max for continuous variables. Tabulations of relative and absolute frequencies will be presented for categorical variables. Incidence rates and 95% CI will be given when appropriate. Subgroup analyses e.g. according to medication (i.e. empagliflozin or SGTL2i or DPP4i or GLP-1 RA), country and physician specialty are planned, as well as per history of CV disease. Descriptive analyses will be supplemented using χ^2 -test or Fisher's exact test for categorical variables and Wilcoxon-Mann-Whitney test for continuous variables. The analyses are purely explorative, hence no correction for multiple testing is needed.

The analyses will relate to the following data as recorded in the eCRF:

1. Patient demographics (age, gender, height, weight, BMI, ethnicity)
2. Time since diagnosis of Type 2 Diabetes
3. Clinical parameters relevant for T2D, CVD, CKD assessment as valid on index date 1
4. Presence of cardiovascular disease and related risk factors at index date 1
5. Presence of chronic kidney disease and related risk factors at index date 1
6. T2D medication the treating physician newly prescribes at study index date 1
7. Reason(s) for treatment decision at index date 1
8. Concomitant T2D medications at study index date 1
9. Concomitant CVD and CKD medications at index date 1
10. Other HCPs involved in treatment decisions at study index date 1 and at index date 2
11. Relevant socioeconomic parameters
12. Discontinuation rate, reason for discontinuation, duration of T2D therapy after one year (± 2 months)

All adverse events and adverse drug reactions collected per study protocol will be included and summarized in the final study report.

For the main analysis data from research question 1 to 5 will be evaluated in a descriptive manner for the total number of prescribed patients enrolled in the study.

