To allow a country specific interpretation of the results, data from research question 1 to 5 will be evaluated in a descriptive manner for the total number of prescribed patients per country enrolled in the study.

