7.4 SECONDARY OUTCOME(S)

All analysis will be descriptive and will be performed on PPS.

[figure not shown]
The prevalence of CVD and CKD will be displayed in frequency tables as well as the reasons for treatment choice, concomitant T2D medication and concomitant CVD/CKD medication. Furthermore other physicians involved in the treatment decision as well as the decision to discontinue the treatment will be given.

The "10 year risk for fatal CVD" will be calculated by applying the SCORE Risk Chart (European Society of Cardiology) taking into account patient's age, gender, systolic blood pressure, smoking status, and total cholesterol value at index date 1.

Moreover, the discontinuation rate and the reason for discontinuation will be displayed in frequency tables.

To assess the duration of T2D therapy after one year (\pm 2 months) the time to discontinuation will be analysed by Kaplan-Meier estimates and subgroups will be compared using log-rank test.

For comparison of subgroups, χ^2 -test or Fisher's exact test, if χ^2 -test is not valid, will be used. If the treatment decision depends on socioeconomic factors will be analysed using χ^2 -test or Fisher's exact test.

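### If drug-class mix and stopping rates vary together by country, the unstratified log-rank test of time to discontinuation can show a class difference that is only country mix (minor)

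*SAP*

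**What the plan says.** SAP 7.4 says of treatment duration that "the time to discontinuation will be analysed by Kaplan-Meier estimates and subgroups will be compared using log-rank test". It names no stratification factor and no adjusted model. The section does not list the subgroups, but SAP 7 does: "Subgroup analyses e.g. according to medication (i.e. empagliflozin or SGTL2i or DPP4i or GLP-1 RA), country and physician specialty are planned". Objective 5 (Protocol 8.2) is itself worded by class, so a log-rank comparison of drug classes is in scope.

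The main analysis takes all countries together: research questions 1 to 5 "will be evaluated in a descriptive manner for the total number of prescribed patients enrolled in the study". SAP 7 then adds a second layer: "To allow a country specific interpretation of the results, data from research question 1 to 5 will be evaluated in a descriptive manner", per country.

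On differences between countries, Protocol 9.9 says "Medication availability might differ between countries due to different reasons (commercial availability, reimbursement status" and adds that this information will be collected under research question 4 to help interpretation. Protocol 9.3.2 includes "financial burden regarding co-payment" among the coded reasons for a patient's request to stop. Protocol 9.5 aims for "at least 500 patients in the GLP1a and at least 1000 patients each in the SGLT2i and DPP4i subgroups" but sets no formal limits on recruitment by medication. Protocol 9.2 requires a site to have access to only two of the three classes. Protocol 9.3.3 marks covariates as not applicable, and item 10.5 of the ENCePP checklist answers No on analytic control of confounding.

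**The concern.** A log-rank test pooled over countries compares each class's observed stoppings with the number expected if every patient at risk, in whatever country, had the same hazard. Suppose one class is used mostly where patients stop more often for reasons unrelated to the drug, such as supply, reimbursement or visit patterns. That class then collects more events than expected, although within every country the classes do equally well.

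The protocol raises the possibility of country differences in access, and nothing in the design balances class mix across countries. Country is recorded, yet the test does not use it. At stake is the reading of a secondary result: a small p-value between classes on persistence would naturally be attributed to the drugs.

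**Working it through.** **Is there a figure to reproduce?** No. The documents give no power, significance level, hazard ratio, discontinuation rate or class mix by country. The sample size is a target, not a calculated number.

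**Inputs from the documents.** "Approximately 4000 patients from 7 countries" (Protocol 4); class minima of 500, 1000 and 1000 (Protocol 9.5), which sum to 2500; follow-up of one year ± 2 months (Protocol 9.1).

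**Assumptions.**
- Seven equal countries; exponential time to discontinuation; no class effect within any country.
- Mean 12-month discontinuation 15%; censoring uniform over days 305 to 425.
- Overall mix SGLT2i 40%, DPP4i 40%, GLP1a 20%. SGLT2i is constant across countries. The GLP1a share falls linearly from the first country to the last, and DPP4i rises by the same amount.
- 5% level.

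N=2500 represents a smaller set at index date 2. With this mix it gives 1000, 1000 and 500 patients per class, exactly the stated minima.

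**Why both must vary.** With equal countries, and no class effect within any of them, the pooled 12-month rate for class j is

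mean rate + Cov(share of j, rate) / mean share of j,

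with the covariance taken over countries. If the share or the rate is constant, the covariance is zero and the pooled rates agree.

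Code the countries x = −1, −2/3, …, 1, so that the mean of x² is 4/9. In the widest scenario the GLP1a share is 0.20 − 0.15x, the DPP4i share 0.40 + 0.15x and the rate 0.15 + 0.10x:
- GLP1a: 0.15 − (0.15 × 0.10 × 4/9)/0.20 = 0.15 − 0.0333 = 0.117
- DPP4i: 0.15 + (0.15 × 0.10 × 4/9)/0.40 = 0.15 + 0.0167 = 0.167

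This is a pooled difference of 5 percentage points with no class effect anywhere.

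**Rejection rates.** There were 1000 simulated data sets per scenario and sample size. The statistic is U′V⁻¹U on 2 degrees of freedom, where U is the vector of observed minus expected events for two of the three classes and V is its variance. The unstratified version computes U and V over all patients. The stratified version computes them within country and then sums. The Monte Carlo standard error is √(0.05 × 0.95/1000) = 0.7 points near 5% and √(0.5 × 0.5/1000) = 1.6 points near 50%.

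| GLP1a share, first to last country | 12-month rate, first to last | Pooled rate DPP4i / GLP1a | N=4000 unstratified | N=4000 stratified | N=2500 unstratified | N=2500 stratified |
|---|---|---|---|---|---|---|
| 20% throughout | 15% throughout | 15.0 / 15.0% | 5.4% | 5.3% | 5.6% | 5.9% |
| 20% throughout | 5 to 25% | 15.0 / 15.0% | 5.6% | 5.4% | 4.4% | 4.2% |
| 35 to 5% | 15% throughout | 15.0 / 15.0% | 6.3% | 6.1% | 4.8% | 4.3% |
| 25 to 15% | 10 to 20% | 15.3 / 14.4% | 7.3% | 5.1% | 4.8% | 3.2% |
| 25 to 15% | 5 to 25% | 15.6 / 13.9% | 13.6% | 4.4% | 10.3% | 5.1% |
| 30 to 10% | 10 to 20% | 15.6 / 13.9% | 13.0% | 4.0% | 12.0% | 5.3% |
| 30 to 10% | 5 to 25% | 16.1 / 12.8% | 45.6% | 4.8% | 31.3% | 6.1% |
| 35 to 5% | 10 to 20% | 15.8 / 13.3% | 26.8% | 3.4% | 19.0% | 5.0% |
| 35 to 5% | 5 to 25% | 16.7 / 11.7% | 83.6% | 4.5% | 61.3% | 4.5% |

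The first three rows are controls, where at most one quantity varies. All of them stay near 5%. In the six rows where both vary, the unstratified test rejects in 7.3% to 83.6% of runs at N=4000, four of the six below 27%, and in 4.8% to 61.3% at N=2500. Stratified by country, the range over all nine rows is 3.4% to 6.1% at N=4000 and 3.2% to 6.1% at N=2500.

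Share and rate move together exactly linearly in these scenarios. That gives the largest covariance for a given spread, so a looser relation would inflate the error less.

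**The case against.** The strongest defence is that the plan is openly descriptive. SAP 7 calls the analyses purely explorative and states no significance level or decision rule. Objective 5 speaks of assessing discontinuation, whereas objectives 1 and 3 also speak of comparing. Pooled persistence by class is a legitimate description of drug use. The authors foresaw country differences and plan a country-by-country evaluation that includes discontinuation, so a careful reader could spot an artefact. SAP 6.4 and 7.5 are not visible in the public text, so further analyses cannot be ruled out.

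Much of this stands, and it sets the priority. It does not remove the point. The explorative label is given as the reason for not correcting for multiplicity and does not address a shifted comparison. The per-country evaluation does not combine the within-country evidence or correct the pooled p-value, and curves by class within country are not spelled out.

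A reader might infer that country is known to drive both the class received and the chance of stopping. The documents do not say so. Availability and reimbursement only might differ, and co-payment burden is a patient-level reason code with no statement that it varies by country. A reader might also infer that the study would declare a false class effect; with no decision rule, the harm is a misleading p-value. Finally, a simplified two-country example with doubled stopping risk and doubled class share gives rejection of about 92%, but that is an extreme case and not the structure of this study.

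**Conclusion.** The point holds in conditional form. The planned class comparison is unstratified and class mix is uncontrolled. A spurious class difference can therefore arise if class mix and discontinuation rate vary by country in a related way; if only one varies, it does not. Under the stated assumptions the error ranges from barely above nominal to very large: about 7% to 84% at N=4000 and 5% to 61% at N=2500. Where in that range the study would fall cannot be settled from the documents.

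The applicable N is itself unclear. SAP 7.4 places these analyses on the prescribed patient set, while SAP 6.3 and 7 place index-date-2 outcomes on the full analysis set. The two should be reconciled.

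Stratifying by country restores the error to about 5% in every scenario. It would be wrong to infer that the stratified p-value then isolates a drug effect, because patient-level differences between users of the classes remain. The priority is minor: an exploratory secondary outcome, with per-country results already planned.

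**What to change.** In SAP 7.4:
- Stratify the drug-class log-rank test by country. Stratifying by physician specialty as well is optional and would need a rule for sparse cells.
- Within the per-country evaluation already planned in SAP 7, present Kaplan-Meier curves by class within each country.
- Keep the pooled class curves as description, without a p-value.
- State that patient-level confounding remains, so the stratified result is still exploratory.

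The cost is SAP wording and a small change to the SAS call. Country is already recorded and is already a planned subgroup, so no new data are needed. The downside is slightly less information from small countries, and none from a country where only one class was started. If the sponsor prefers pure description, dropping the class p-value altogether would also remove the problem.

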9.2 SETTING

Data collection from approximately 4000 patients from up to 8 countries is planned. Site selection will be performed to reflect routine T2D care in the participating countries in order to secure representativeness of the T2D population. The following countries will participate in this non-interventional study: Bulgaria, Czech Republic, Hungary, Poland, Russia, Serbia, Slovenia.

A log of all patients included into the study (i.e. having given informed consent) will be maintained in the Investigator Site File (ISF).

Boehringer Ingelheim reserves the right to discontinue the study or to remove a patient at a particular study site for the following reasons:

1. Failure to meet expected enrollment goals overall or at a particular study site.
2. Emergence of any efficacy/safety information that could significantly affect continuation of the study, or any other administrative reasons, i.e. lack of recruitment.
3. Violation of the protocol, the contract, or applicable laws and regulations for non-interventional studies, which could disturb the appropriate conduct of the NIS.

Site selection:

Office based HCP of different medical specialties (endocrinologist, diabetologist or cardiologist) will be requested in order to check for feasibility prior to site selection. Amongst other criteria, sites will be eligible if HCPs have access and can prescribe at least 2 of the T2D drug classes of interest (SGLT2i, DPP4i and/or GLP1a). Sites will also be asked for the number of expected patients meeting inclusion/exclusion criteria in a given time window (1 month September 2018) by means of being newly initiated with empagliflozin or other SGLT2i, DPP4i or GLP1a in September 2018. In case that more than a representative number of sites which will be assessed during the feasibility, are signaling their willingness to participate in the study, the sites will be randomly selected.

To get basic information into demographics for site distribution, data on physicians' age, gender, office postal code will be collected.

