9.12 BIAS

Selection bias could occur at the site level and the patient level.

To minimize the site level selection bias, sites will be eligible if HCPs initiate second line medications in their T2D patients. In addition to that, the number of proposed sites will be 150% of sites to be finally included which will allow random selection of site.

In order to limit the variability of outcomes, sites will be eligible if they have access and can prescribe at least 2 of the T2D drug classes of interest (SGLT2i, DPP4i, GLP1a) for the targeted T2D.

To minimize selection bias at the patient level, physicians are requested to include all patients meeting inclusion and exclusion criteria in the study period of 4 months (September – December 2018) into the study. However, there may be a bias regarding patient groups at index date 1 and 2, since not all patients who have consented to documentation at index date 1 may or can give their consent (e.g. due to death or loss to follow-up) to further documentation at index date 2.

Information bias will be minimized by the use of standard eCRF and physicians' training on the study protocol and handling of the eCRF.

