7.3 PRIMARY OUTCOME

For the primary outcome, the baseline characteristics will be analysed in a descriptive manner. Frequencies and 95% CI will be given when appropriate.

In addition the baseline characteristics will be compared by medication, physician speciality and country using χ^2 -Test or Fisher's exact test, if χ^2 -Test is not valid, for categorical variables and Wilcoxon-Mann-Whitney test for continuous variables.

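### SAP 7.3/7.4 give no visible site-clustering rule for 95% CIs or for country and specialty comparisons, and no combined country-stratified test for objective 4

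*SAP*

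**What the plan says.** **Analysis.** Under SAP 7.3, "the baseline characteristics will be compared by medication, physician speciality and country" with chi-square or Fisher's exact tests for categorical variables and Wilcoxon-Mann-Whitney for continuous ones. The same section adds: "Frequencies and 95% CI will be given when appropriate". It names no interval method. In SAP 7.4, time to discontinuation is compared between subgroups by log-rank test, and the objective-4 sentence reads "If the treatment decision depends on socioeconomic factors will be analysed using" a chi-square or Fisher's exact test. SAP 6.5, on pooling of centres, is marked not applicable. SAP 7 adds a descriptive evaluation of research questions 1 to 5 for each country and calls all analyses explorative, giving that as the reason for no multiplicity correction.

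**Sampling.** Protocol 9.2 says that, if more sites than needed are willing, "the sites will be randomly selected". Protocol 9.12 plans for this: "the number of proposed sites will be 150% of sites to be finally included which will allow random selection of site". Within a site, "physicians are requested to include all patients meeting inclusion and exclusion criteria".

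**Size.** Protocol 9.5: "No formal sample size calculation is provided for this study". The target of about 4000 is justified partly by physician-specific and country-specific analyses.

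**The concern.** Sites are chosen first, and each then enters all its eligible patients. Patients of one practice share prescribers, referral routes and local policy, so their characteristics may be correlated. The named tests treat patients as independent. Country is constant within a site, so a country comparison is a comparison of groups of whole sites. The same holds for specialty if each site is a single-specialty practice, which is an assumption here. These are the comparisons in which ignoring clustering does most harm. Characteristics that vary within a site, such as the drug prescribed or a socioeconomic factor, are much less exposed.

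Objective 4 raises a separate question. Protocol 9.9 says drug availability and reimbursement may differ between countries. If socioeconomic factors differ between countries too, a pooled test could show an association present in no country, or weaken one present in all.

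Precision was not estimated in advance (protocol 9.5; ENCePP checklist item 10.2 is marked N/A). Readers will therefore judge it from the printed CIs and p-values.

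**Working it through.** The plan has no precision figure to reproduce. The check asks what the stated methods would deliver.

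**Inputs from the documents.** N about 4000; seven named countries (protocol 9.2); three specialties; 34% CVD prevalence, a Swedish background figure in protocol 8.1 used only as an illustration.

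**Assumed inputs, because none is given.** Patients per site m = 10, 20 or 40 (about 400, 200 or 100 sites); within-country ICC 0.01, 0.05 or 0.10.

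**Formulas.**
- Design effect: DE = 1 + (m − 1) × ICC. Low 1 + 9 × 0.01 = 1.09; mid 1 + 19 × 0.05 = 1.95; high 1 + 39 × 0.10 = 4.9.
- Effective N: 4000 / DE.
- Ordinary half-width: 1.96 × √(0.34 × 0.66 / 4000) = 1.47 points; the clustered value multiplies this by √DE.
- Coverage of an ordinary 95% CI: 2Φ(1.96/√DE) − 1.
- True error of a nominal 5% chi-square test between groups of whole sites: P(χ² with df degrees of freedom > 5% critical value / DE).

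| | Low | Mid | High |
|---|---|---|---|
| Design effect | 1.09 | 1.95 | 4.9 |
| Effective N | 3670 | 2051 | 816 |
| Clustered half-width (points) | 1.53 | 2.05 | 3.25 |
| Coverage of ordinary 95% CI | 94.0% | 84.0% | 62.4% |
| Error, three specialties (2 df) | 6.4% | 21.5% | 54.3% |
| Error, seven countries (6 df) | 7.3% | 37.4% | 86.1% |

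At 10 patients per site and ICC 0.05, coverage is 89.6% and the seven-country error 19.2%.

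**Simulation check** (beta-binomial, 4000 replicates, seven fixed countries).
- Ordinary chi-square error for seven countries: 7.4% / 37.6% / 85.5%, in line with the formula.
- Rao-Scott test with site as cluster: 4.5% to 5.9% in every case tried.
- Ordinary chi-square for a factor that varies within sites: 4.9% / 5.4% / 9.7%.
- Overall CIs when countries differ (logit SD 0.25 to 0.5): site as cluster alone over-covers at about 96% to 98%; adding country as stratum gives 94% to 95%.

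**Objective 4** (4000 replicates, 7 × 571 patients, binary drug and factor centred at 50%, shares varying independently by country, no association within any country).

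| Country spread (logit SD) | 0 | 0.25 | 0.3 | 0.5 | 0.75 |
|---|---|---|---|---|---|
| Pooled test rejects | 5.0% | 6.6% | 8.3% | 20.7% | 44.9% |

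A country-stratified Cochran-Mantel-Haenszel (CMH) test rejects in 4.6% to 5.7% throughout. With an assumed within-country odds ratio of 1.25, power at SD 0.25, 0.5 and 0.75 is 92.3%, 80.1% and 71.6% pooled, against 93.5%, 91.8% and 87.0% stratified.

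**The case against.** **No inputs.** One might infer that the planned p-values are certainly too small. The documents do not support that. They give no ICC, site count or patients per site, and in the low case the effect is trivial. What remains is a conditional statement.

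**Target of inference.** About two thirds of the proposed sites are kept (100/150). If results were meant only for those proposed sites, and all eligible patients consented, a finite-population factor of 1/3 would apply. The design effect becomes about 0.36 / 0.65 / 1.63 and ordinary coverage above 99% / 98.5% / 87.5%, so the concern largely disappears. However, protocol 9.2 says site selection should mirror routine care in the participating countries, which points to a wider target. For that target the factor does not apply, although the sites are then not a random sample of it either. The protocol also does not say that random selection is made within each country; using country as a stratum is an inference from the fixed list of countries.

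**Objective 4.** One might also infer that the pooled test is biased. That is not shown. The objective is to describe an association, and type of insurance is itself a listed factor, so a marginal answer is legitimate. Protocol 9.9 does not say that socioeconomic factors differ by country. Per-country results are planned and would partly expose any mixing; they do not give one within-country answer.

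**Medication comparisons.** Protocol 9.2 says "sites will be eligible if HCPs have access and can prescribe at least 2 of the T2D drug classes", so a site may lack one class and drug choice may be partly fixed by site. These comparisons are less affected, not immune.

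**Explorative status.** No decision rests on a p-value, CIs are given only when appropriate, and point estimates of overall frequencies are unaffected. This lowers the importance. It does not make a printed 95% CI cover 95%.

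**Blacked-out text.** SAP 6.4 and 7.5 have no visible content, so the point is limited to the visible text.

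**Conclusion.** The point holds conditionally. For results meant to apply beyond the proposed sites, any positive ICC makes ordinary CIs for overall frequencies too narrow and p-values for country comparisons too small; the same goes for specialty if sites are single-specialty. Under the assumed ranges this runs from negligible to large, and the documents cannot narrow it. The log-rank test shares the problem when the subgroups are countries or specialties.

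For objective 4, the pooled test describes the marginal association and should stay. What is missing is a combined within-country result beside it. The possible distortion is small if country differences are small: at most 8.3% error up to logit SD 0.3 in the simulation, which rests on equal country sizes and 50% shares.

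Overall importance is minor to moderate.

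**What to change.** Amend SAP 6.5, 7.3 and 7.4:

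- Compute 95% CIs of overall frequencies with site as cluster and country as stratum (for example PROC SURVEYFREQ).
- Make country and specialty comparisons with site as cluster: Rao-Scott chi-square for categorical variables, GEE or a mixed model with site for continuous ones.
- For time to discontinuation by country or specialty, report a Cox model with site-robust variance alongside the log-rank test.
- For objective 4, keep the pooled and per-country tables and add a country-stratified CMH test or a model with country. Note that it is uninformative for factors nearly constant within a country.
- Replace the not-applicable entry in SAP 6.5 with these rules.
- Report the number of sites and the distribution of patients per site.

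The cost is SAP wording and standard SAS procedures, using site and country identifiers that the study should already hold. No new data are needed. The downside is wider CIs and some sparse country strata. If clustering proves negligible, the results will hardly change.
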